12.5.3 Analysis of safety

The overall percentage of participants with at least one local adverse event (solicited or unsolicited) and the percentage with at least one general adverse event (solicited and unsolicited) during the 7-day surveillance period after vaccination will be tabulated. The incidence, intensity and relationship of individual solicited symptoms over the 7-day surveillance period will be calculated per group and vaccine administration.

The number of participants with at least one report of an unsolicited adverse event, classified by WHO-preferred terms, reported up to 29 days after vaccination will be tabulated per group and vaccine administration. The intensity and relationship to vaccination of the unsolicited symptoms reported will also be assessed.

Serious adverse events are expected to be rare, but where observed will be described. Comparisons between study groups of incidence of symptoms, local and general symptoms will be made based on a two-sided Fisher's Exact Tests. Analysis of safety during the 12-month surveillance period will consist of comparison of incidence of serious adverse events as well as hemoglobin, creatinine and ALT levels.

Clinical laboratory parameters

Hematological (CBC) and biochemical (ALT, creatinine) laboratory parameters will be measured at specific time points, Days 0, 7, 14, 30, 37, 44, 60, 67, 74, 90 and starting on day 180 every 3 months. Clinically relevant abnormal values will be tabulated and a trend analysis could be performed if deemed necessary.

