All Adverse Events were expected except the one SAE. Dose escalation was held until relationship of the SAE to vaccination could be established. Evaluation of the volunteer was completed and it was determined the event was not vaccine related. A final SAE report was submitted. No protocol revisions have been made in response to AEs.

Group	A = low dose	B = medium dose	C = high dose
Number of subjects	8	8	7
Total immunizations	22	22	19
Grade 1 reactions	11	20	26
Grade 2 reactions	6	17	21

Adverse Events by group are summarized below:

This study used 0.5 mL of AS02A for each dose level of FMP2.1. For reasons of simplicity of reconstitution and administration, it was decided to reduce the volume of AS02A

Page 21 of 96 Version 17, DEAP/MRTC/MMVDU CONFIDENTIAL

proportionate to the reduction of FMP2.1 antigen from the full dose in future trials. Thus for the present trial each vial containing 50 µg of FMP2.1 will be reconstituted with 0.5 mL of AS02A from a prefilled syringe as described in Section 9.2.1.

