4.3.11 Safety of RabAvert® rabies vaccine

Local and/or mild systemic reactions may occur after injection of RabAvert® rabies vaccine but these are usually transient and do not contraindicate continuing immunization. Local reactions such as induration, swelling and reddening have been reported more often than systemic reactions. In a comparative trial in normal volunteers, Dreesen *et al.* (52;60) described their experience with RabAvert compared to a HDCV rabies vaccine. Nineteen subjects received RabAvert and 20 received HDCV. The most commonly reported adverse reaction was pain at the injection site, reported in 45% of the HDCV group, and 34% of the RabAvert group. Localized lymphadenopathy was reported in about 15% of each group. The most common systemic reactions were malaise (15 % RabAvert group vs. 25 % HDCV group), headache (10 %

RabAvert group vs. 20 % HDCV group), and dizziness (15 % RabAvert group vs. 10 % HDCV group). In a recent study in the USA (4), 83 subjects received RabAvert and 82 received HDCV. Again, the most common adverse reaction was pain at the injection site in 80% in the HDCV group and 84% in the RabAvert group. The most common systemic reactions were headache (52% RabAvert group vs. 45% HDCV group), myalgia (53% RabAvert group vs. 38% HDCV group) and malaise (20% RabAvert group vs. 17% HDCV group).

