4.3.12 Rationale for double blind controlled design

A double-blind controlled dose escalation trial will allow assessment of vaccine safety in each of three groups, one group each to receive medium and full dose levels of the experimental vaccine, and one group to receive the comparator vaccine. Thirty adults will be randomized to receive the medium dose level of FMP2.1 (n=20) or rabies vaccine (n=10) and thirty to receive the full dose level of FMP2.1 (n=20) or rabies vaccine (n=10). The division of the rabies group into two groups of ten is done to maintain blinding at each immunization time point, and all participants who receive the rabies vaccine will be analyzed as a single group. The sample size of the groups, however, will not allow detection of anything other than very large differences in the occurrence of adverse events among the three groups. The advantage of double blinding is to remove the potential for investigator and participant prejudgment about the effects of the vaccines in the reporting of adverse events.

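### Section 12.5.3 compares groups on symptom incidence only; the 0–3 intensity grades enter no between-group comparison, so a shift from mild to more severe local reactions can go unregistered

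*Combined protocol and SAP*

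**What the plan says.** Section 12.5.3 of the protocol does three separate things with reactogenicity data.

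- It tabulates participant-level percentages: "The overall percentage of participants with at least one local adverse event (solicited or unsolicited) and the percentage with at least one general adverse event".
- It summarises each solicited symptom: "The incidence, intensity and relationship of individual solicited symptoms over the 7-day surveillance period will be calculated per group and vaccine administration".
- It tests: "Comparisons between study groups of incidence of symptoms, local and general symptoms will be made based on a two-sided" Fisher's exact test.

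The test sentence names no grade threshold, no unit (symptom, dose or participant) and no significance level. The natural reading is any-grade occurrence. Intensity is graded 0–3 for every solicited symptom (10.2, Table 5), but 12.5.3 uses it only in summaries.

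The groups are 20 v 20 v 20. For the 25 µg cohort, "Thirty adults will be randomized to receive the medium dose level of FMP2.1 (n=20) or rabies vaccine (n=10"); the 50 µg cohort is built the same way, and "all participants who receive the rabies vaccine will be analyzed as a single group" (4.3.12).

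On how common reactions are, 4.3.11 gives two different pictures for RabAvert. In the larger study (83 RabAvert recipients), "the most common adverse reaction was pain at the injection site in 80% in the HDCV group and 84% in the RabAvert group". In the smaller one (19 recipients), pain was "reported in 45% of the HDCV group, and 34% of the RabAvert group".

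**The concern.** The primary objective (5.1) is to evaluate safety and reactogenicity of each dose level compared with rabies vaccine. Two reactogenic vaccines may differ little in whether a recipient reacts at all and much in how strongly. A test of occurrence sees only the first difference. If most rabies recipients already have some local reaction, there is little room above them, and a vaccine that turns mild reactions into ones that interfere with daily activity could yield a non-significant comparison in the Primary Study Report. Section 12.5 says the day-90 data feed decisions on the development plan. The grades are collected, but without a pre-specified severity comparison any grade cut-off could be chosen after unblinding.

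**Working it through.** **The plan's own figure.** Table 6 (12.4) gives the chance of at least one event in 20 as 1 − (1 − p)^20. For p = 0.01, 0.05, 0.08 and 0.10 this is 0.182, 0.642, 0.811 and 0.878, which match the printed values. The plan gives no power for the Fisher tests, so there is nothing further to reproduce.

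**Inputs.** n = 20 per group (4.3.12); RabAvert pain 84% or 34% (4.3.11); two-sided level 0.05, assumed because none is stated. Fisher power is exact: sum Bin(a; 20, p1) × Bin(b; 20, p2) over all (a, b) with Fisher p ≤ 0.05.

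**Any-grade local comparison, vaccine v rabies.**

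If all 20 vaccinees react:
- rabies 17/20 gives p = 0.23
- rabies 16/20 gives p = 0.11
- rabies 15/20 gives p = 0.047

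At 84% the expected rabies count is 0.84 × 20 = 16.8. Power when every vaccinee reacts is therefore Pr(Bin(20, 0.84) ≤ 15) = 0.21.

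| Rabies rate | Vaccine rate | Power |
|---|---|---|
| 84% | 90% | 0.04 |
| 84% | 95% | 0.09 |
| 84% | 98% | 0.15 |
| 84% | 100% | 0.21 |
| 34% | 90% | 0.96 |
| 34% | 95% | 0.99 |

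The ceiling depends on which cited rate applies. If the 34% were a per-dose rate (an assumption), three independent doses would give 1 − 0.66³ = 71% per participant.

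**General symptoms.** Named symptoms after RabAvert run from 10% (headache, smaller study) to 53% (myalgia, larger study). RTS,S/AS02A in Gambian adults gave headache 34% and malaise 25% (4.3.7). At a rabies rate of 52%, power is 0.70 against 90% and 0.87 against 95%. No ceiling is documented here.

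**What a maximum-grade comparison would add.** The documents give no grade distribution per participant for either vaccine, so the distributions below are assumptions. Rabies is fixed at 16/64/16/4% for grades 0/1/2/3. The rank column is a tie-corrected Mann–Whitney test, by simulation (10,000 runs; null rejection about 0.05).

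| Vaccine, grades 0/1/2/3 | Any-grade Fisher | Grade 2+ Fisher | Rank test |
|---|---|---|---|
| 2/38/40/20% | 0.15 | 0.65 | 0.83 |
| 5/55/30/10% | 0.09 | 0.19 | 0.36 |
| 16/44/30/10% | 0.02 | 0.19 | 0.18 |

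The second row is the milder shift, with power of about 0.35. In the third row the any-grade rate is the same in both arms and only severity moves. The incidence test then rejects at its own null rate.

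A single severity threshold also finds only large differences: against a vaccine rate of 30%, Fisher power is 0.76, 0.45 and 0.24 for rabies rates of 0%, 5% and 10%.

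**25 v 50 µg.** The US Phase 1 table, just before 4.3.5, reads "Grade 1 reactions 11 20 26" across low, medium and high dose, with 6, 17 and 21 grade 2 reactions. These are counts of reactions in 8, 8 and 7 people. The grade 2 share is 17/37 = 46% at medium dose and 21/47 = 45% at high dose, so the mix does not differ. Treating counts as Poisson per person (which ignores clustering):
- any reaction: 1 − e^(−37/8) = 0.990 v 1 − e^(−47/7) = 0.999
- grade 2: 1 − e^(−17/8) = 0.88 v 1 − e^(−21/7) = 0.95

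Power is then 0.00 for any-grade Fisher, 0.03 for grade 2+ Fisher and about 0.09 for the rank test. On that model the grade-based test saturates too.

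**The case against.** The best defence is that severity is not hidden. Intensity is reported per group and per dose, grade 3 events go to the safety committee regardless of relationship (15.4), and severe local reactions are individually evaluated before further vaccination (6.6). Sections 4.3.12 and 12.4 say that only very large differences are detectable, so a non-significant result is not offered as evidence of similarity. A final analysis plan is still to be agreed (12.5). All of this stands, and it limits the point to a missing pre-specified comparison. It does not remove it. The power caveat in 12.4 concerns differences in incidence, and 12.5 says only that the later plan will cover events by dose and number of vaccinations.

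Three stronger readings are tempting, and the documents do not support them.

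- **That any-grade incidence is near its ceiling in every arm.** The 34% figure and the general-symptom rates contradict this, and no participant-level rate is given for FMP2.1.
- **That the percentages with at least one event are the tested endpoint.** They are tabulated. The Fisher sentence may equally mean individual symptoms, perhaps per dose, which would be less saturated than a composite over three doses.
- **That the 25 v 50 µg contrast cannot show a difference, that grades would rescue it, or that it sets the dose for children.** The US counts are not participants and do not separate local from general reactions. That trial also used 0.5 mL of AS02A at every dose level, whereas here 25 µg comes with 0.25 mL. Section 4.3.9 assigns dose selection to a later paediatric study.

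**Conclusion.** The point holds in limited form, as a cheap improvement. Section 12.5.3 specifies no between-group comparison that uses intensity. Where any-grade local reactions to RabAvert are near 84%, the local comparison with FMP2.1 has at most about 21% power and is blind to a shift from grade 1 to grades 2–3. At 34% the ceiling disappears, although an incidence test still carries no information on grade. For vaccine v rabies, a maximum-grade test could raise power from 0.15 to 0.83 under a large assumed shift, or from 0.09 to about 0.35 under a milder one. These figures rest on a 0.05 level that the plan does not state and on grade distributions that the documents do not supply. No gain is claimed for 25 v 50 µg.

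**What to change.** In 12.5.3:

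1. State that the existing Fisher tests are any-grade, and keep them.
2. Add a pre-specified comparison of each participant's maximum solicited grade (0–3) over the 7-day windows, local and general separately, by an exact ordered-category (Wilcoxon) test.
3. Report by group the proportions at grade 2 or higher and at grade 3, with confidence intervals.

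The cost is a few sentences and table rows, since Table 5 grades are already collected. The downsides are modest. Pain and most general symptoms are graded partly on self-reported interference with activity (swelling, erythema, arm motion and temperature are measured). A further comparison is added. With 20 per group, only large differences remain detectable.

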13 SITE MONITORING PLAN

Site monitoring may be conducted by DMID or its designated monitoring contractor, to ensure that GCP standards and regulatory guidelines are being followed. Pre-trial monitoring visits will be made to the site, including the clinical laboratory. All records will be made available to monitors, including regulatory files, CRFs and other source documents, QA/QC documentation, SOPs, etc. At the discretion of the monitor, additional site visits may be made during the course of the trial and at the end of the surveillance period.

In addition, monitors from USAMMDA, GSKBio and WHO will be welcome to make site visits, in coordination with the primary monitoring group designated by DMID.

In conjunction with the monitoring body designated by DMID, a detailed monitoring plan, subject to approval by OCRA, will be developed and included in the Manual of Procedures. The monitoring plan will include the number of subject charts to be reviewed, which/what proportion of data fields and what will be monitored, and who will be responsible for conducting the monitoring visits, and who will be responsible for ensuring that monitoring findings are addressed.

Page 61 of 96 Version 17, DEAP/MRTC/MMVDU CONFIDENTIAL

14 QUALITY CONTROL AND QUALITY ASSURANCE

SOPs for quality management will be developed, used to train appropriate personnel, and kept on file with documentation of training. Data will be evaluated for compliance with protocol and accuracy in relation to source documents. The study will be conducted in accordance with procedures identified in the protocol. The types of materials to be reviewed, who is responsible, and the schedule for reviews will be referenced in the SOPs. Study-specific training will be provided for all staff prior to the commencement of the trial.

The study will be conducted at a single center, the Bandiagara Malaria Project in Bandiagara, Mali, with the exception of immunological studies which will be conducted at WRAIR (serology, GIA and CMI), UMB (CMI) and the main campus of the University of Bamako (serology NOT to be used for study endpoints, and CMI).

SOPs will be used at all clinical and laboratory sites. Regular monitoring and an independent audit will be performed according to GCP/ICH (e.g., data monitoring). Following written standard operating procedures, the monitors will verify that the clinical trial is conducted and data are generated, documented (recorded), and reported in compliance with the protocol, GCP, and the applicable regulatory requirements. Reports will be submitted to DMID on monitoring activities.

The investigational site will provide direct access to all trial related sites, source data/documents, and reports for the purpose of monitoring and auditing by the sponsor, and inspection by local and regulatory authorities.

The MRTC Biostatistics and Epidemiology Unit (Data Coordinating Center) in Bamako will implement quality control procedures beginning with the data entry system and generate data quality control checks that will be run on the database. Any missing data or data anomalies will be communicated to the field site for clarification/resolution.

15 ETHICAL CONSIDERATIONS

15.1 Statement of compliance and ethical reviews

The WRAIR FMP2.1/ASO2A vaccine has been submitted as FDA IND BB-9202 and the study described in this protocol will be conducted according to current Good Clinical Practices (US 21 CFR Part 50-Protection of Human Subjects and Part 56-Institutional Review Boards, U.S. Army Regulation AR 40-38 and AR 70-25, U.S. 45 CFR 46, 21 CFR 312, and the applicable rules and regulations of Mali).

The FMPOS IRB (FWA00001769) will review and approve the protocol prior to study start. In addition, the study will be reviewed by the Human Subjects Research Review Board (HSRRB) of the Office of the Surgeon General, US Army, by DMID, and the University of Maryland IRB. Documentation of the approval by these ethical review boards will be kept in the PI's study file.

15.1.1 Institutional Review Boards

All amendments will be submitted to the University of Bamako Faculty of Medicine Pharmacy and Odonto-stomatology (FMPOS) IRB, the UMB IRBs, and the HSSRB as well as to the DMID as the study sponsor. No amendments will go into effect without written approval from the FMPOS IRB, the UMD IRB, HSRRB and DMID except when necessary to eliminate immediate hazards to the participants. Protocol deviations will also be reported to each IRB according to the policy of each IRB. CRFs and other source documents will be examined to

Page 62 of 96 Version 17, DEAP/MRTC/MMVDU CONFIDENTIAL

determine whether missing data were not transcribed, unavailable or missing for unknown reasons and this information will be coded and documented in the database.

The investigators will inform all the IRBs and DMID of the following:

- All subsequent protocol amendments, informed consent changes or revisions of other documents originally submitted for review
- Serious and/or unexpected adverse events occurring during the study, where required
- New information, including any provided by GSKBio, USAMMDA or WRAIR, that may affect adversely the safety of the participants or the conduct of the study
- An annual update and/or request for re-approval, where required
- When the study has been completed.

15.2 Informed consent

The principles of informed consent in the current edition of the Declaration of Helsinki will be implemented before any protocol-specified procedures or interventions are carried out.

Information will be given in both oral and written form whenever possible. The written consent documents will embody the elements of informed consent as described in the current edition of the Declaration of Helsinki, will adhere to the ICH Harmonized Tripartite Guideline for Good Clinical Practice and will also comply with applicable Malian regulations. Independent witnesses will be used to attest that illiterate potential participants have understood the contents of the informed consent.

15.2.1 Screening and study informed consent

We consider informed consent to be a dynamic, ongoing process, with continuous availability of investigators to answer any questions that arise in the course of the trial and to ensure that participants understand trial procedures. Should new data become available that could affect participant safety and/or willingness to continue in the study, informed consent would be obtained and documented again.

The extensive contact between the team of investigators and the population of Bandiagara has led to the development of mutual trust and the establishment of an ongoing informed consent process attempting to address issues related to interventional studies in resource-limited settings. Many discussions with local community leaders, heads of families and citizens through group meetings, and more limited group interviews have reviewed the need to obtain a written informed consent from study participants. The community has now become familiar with the informed consent process, including written, signed consent forms, which have been used for several studies at this site, including the ongoing Phase 1 malaria vaccine trial that began in 2003.

Prior to initiating any study in Bandiagara, the senior Malian and U.S. investigators visit the local commandant (representative of the national government), the mayor, the director of the local school system, the chiefs of each of the eight quartiers of Bandiagara, the medical director of the local health center, the director of the Bandiagara Center for Research of Traditional Medicine, and the head of the Bandiagara traditional healers' association. These are courtesy visits in which results of the previous year's studies are summarized and plans for new studies are explained and any questions are answered. In accordance with the tradition in Mali, small quantities of kola nuts are given to the chiefs of the quartiers and the traditional healers as a sign of respect.

Page 63 of 96 Version 17, DEAP/MRTC/MMVDU CONFIDENTIAL

These individual meetings are followed by a larger community meeting attended by the above personages as well as numerous other local health care providers, traditional healers and notable citizens (including several respected women from the community). Planned studies are explained in more detail, and ample time is given for carefully and thoroughly addressing all questions and concerns. This question and answer period is frequently prolonged with many detailed and often sophisticated questions being raised. Each presentation, question and response is translated from French into Dogon and Peulh so that all present understand the entire discourse.

Once this group of community leaders has expressed their approval of the planned study, they disseminate information to their various constituencies, so that when potential recruits are approached by study staff they are already generally aware of the nature of the impending study. The investigators do not consider this process to constitute "community consent" in addition to or in lieu of individual informed consent, but rather a community "permission to enter" that is a necessary prerequisite to conducting any study in a tight-knit and highly organized traditional rural community such as Bandiagara.

After community meetings have been held, a brief announcement is made on local radio describing the study. Prior to initiating screening and informed consent, the study team meets to review the oral translation of the consent forms into the relevant local languages and dialects word by word, until there is consensus that the individuals responsible for giving consent in each language are conveying as accurately as possible the exact content of the IRB-approved French language consent form.

A period of approximately two weeks is allotted for screening and recruitment to allow plenty of time for participants to consider their decision about participating and to discuss their participation with family members and others in the community. At the times of screening and recruitment, the consent forms are read to participants who speak French, and translated orally into the language of choice of each participant. In all cases, the investigator will give the participants ample opportunity to inquire about the details of the study and to ask any questions before dating and signing the consent forms, including the opportunity to take a copy of the consent form home to review with family members or others before returning on a later day with their decision. All illiterate individuals will have the study and consent forms explained to them point by point by the interviewer in the presence of a witness who will sign the consent form. Witnesses will have no association with the conduct of the study and will not be related to the study subject.

We will adapt a comprehension test recently piloted in another vaccine trial in Mali. Volunteers must answer all questions on the comprehension exam correctly prior to being eligible for enrollment to the study. Study staff will use incorrect answers to identify those areas of the informed consent that need further review with the volunteer. The incorrectly answered questions will then be repeated to the volunteer after a review of the informed consent. A final score of 100% will be required for the volunteer to be considered eligible to continue the screening process. This test will be administered orally in the presence of a witness in the case of potential volunteers who cannot read.

Informed consent will be documented by the use of a written consent form approved by the IRBs and signed or thumbprinted and dated by the participant, and by the person who conducted the informed consent discussion. Thumb printing will be used for illiterate persons, who are expected to constitute the majority of participants. The consent will be orally translated into native languages from the French written version of the consent form. The consent will be administered by a study clinician who is fluent in French and will either be fluent in the local language of the participant or use a translator. A witness will assist during the procedure. After the participant clearly states that she/he has understood what was explained and agrees to participate to the study, the consent forms will be completed. The participant will be asked if

Page 64 of 96 Version 17, DEAP/MRTC/MMVDU CONFIDENTIAL

she/he prefers to thumbprint or to sign. In the case of the thumbprint option, the distal end of her/his left thumb will be applied to a stamp inker and then firmly applied to the space on the consent forms reserved for thumbprints. This procedure has been followed for many years by the BMP team, and thumbprints are uniformly legible.

The signature/thumbprint confirms that the consent is based on information that has been understood. Each participant's signed informed consent form is kept on file by the investigator for possible inspection by regulatory authorities. The subject will receive a copy of the signed and dated written informed consent forms and any other written information provided by the investigator, and will receive copies of any signed and dated consent form updates and any amendments to the written information.

Since the vast majority of study participants do not use telephones, fax or mail, contact information is provided in terms of local physicians who can be visited directly and who can themselves reach the investigators directly or by telephone or fax.

